4.2 Project Outcomes

Primary Endpoint:

- Correlation of sonographic estimated gastric volume with volume aspirated through a naso- or oro-gastric tube, that was placed by routine.

Secondary Endpoints:

- Performance over time, improvement of examination technique, critical number of examinations to achieve a high quality standard (>80% congruence for estimated and aspirated gastric volume in fluids).
- Association of performance with experience, residents vs. attendings.
- Number of patients classified as empty -> possible implications for management and induction.
- Number of patients with full stomach -> possible implications for management and induction.
- Time used for examinations, time used with growing experience.
- Estimated aspiration risk vs. sonographic gastric volume.
- Total number of pulmonary aspirations.

5 Project Description

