7.2 Exclusion Criteria

If a subject fulfils any of the following exclusion criteria he/she may not be included:

- Life threatening/ time critical emergency interventions, graded followingly according to the Swiss Society for Anaesthesiology and Resuscitation (A-QUA): Notfall <1h, vital (sofortiger Eingriff notwendig)
- Known pregnancy
- Obstetric surgery
- Underage (< 18 years)
- Absence of informed consent (missing or inability to provide)
- No anaesthetist with completed structural education is available.
- Contraindications for naso- or orogastric tubes or inability to correctly place such.

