Tutors/experts are all expert sonographers on different modalities. They will receive a preceding 240 minutes training, consisting of a 60 minutes theoretic introduction and a 60 minutes course by a radiologist and abdominal sonography expert, certified by the Swiss Society for Sonography. The remaining time will consist of individual exercise on healthy volunteers and at least 10 trial sonographies with gastric volume calculation under supervision of another member of the tutor group.

Our study will be performed mainly in the induction rooms of our operating unit and occasionally inside the operating theatre. Standard care will be given to every patient at the usual location, with our usual equipment (anaesthetic machine, monitoring, medication and airway devices and so on) and by our usual anaesthesiologic team members. Sonographic examination and determination of the gastric content will be executed on one of our standard ultrasound machines (Venue and LOQIC e from GE-Healthcare®) with a curved array low frequency (2-10 Hz) abdominal probe or our portable ultrasound devices (IQ+ from Butterfly Network Inc.®).

Before performing the sonographic examination, the responsible anaesthesiologist will be asked to rate the estimated risk of pulmonary aspiration, based on personal impression, patient history and clinical finding. All anaesthetists are advised to perform the examination only if they could guarantee privacy before they expose patient abdomen for the examination. Primarily, a qualitative assessment of the gastric content should be performed in supine and right-lateral decubitus (RLD) position. In low volume states a right-lateral decubitus position (RLD) has the advantage of a gravitational shift to the antrum. That is why we plan to perform the examination in both positions. If RLD position is not possible due to patient factors a half sitting position can be tried. Gastric content will be classified into empty, fluid, solid or mixed. Examiners will be asked to classify sonographic conditions into poor, medium or good and provide a reason in case of limited conditions. If fluid gastric content is detected an estimation of the quantity should be performed as follows.

After identification, CSA will be measured and gastric content is estimated by implementation of the formula described by Perlas et al: ^{20, 28}

$$\text{Gastric Volume (ml)} = 27.0 + 14.6 \times \text{right-lateral CSA (cm}^2\text{)} - 1.28 \times \text{age (years)}.$$

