This model is based on gastroscopic fluid assessment and highly validated by several publications. ²⁸

After placement of the routine naso- or orogastric tube, which is a standard procedure for both RSIs and advanced laryngeal masks at our institution - we compare the calculated and effective suctioned volume of the gastric content and analyse the difference and quality of the sonographic measurement. In some patients a gastric tube is contraindicated or not possible to place correctly. In this case an exclusion of the study is mandatory according to our exclusion criteria. Patients planned for an intervention in a regional anaesthesia will not receive a gastric tube.

In exceptional cases the responsible anaesthesiologist is allowed to upgrade patients from an advanced laryngeal mask to an RSI after ultrasound performance to ensure patient safety. Downgrading from RSI to advanced laryngeal masks on base of the ultrasound results is not allowed.

All data concerning the sonography will be noted in a password protected Excel sheet only available to institute members by the responsible anaesthesiologist performing the examination. Background patient data including demographic data are collected during the structured preoperative anaesthesiologic assessment according to in house standard procedures and data management. Data will be coded and condensed in a password-protected Excel File, only accessible to study personnel. A patient identification log will be kept in a locked archive for data verification processes only. To guarantee seamless traceability we will create a immutable PDF file after all relevant changes or at least once per month and store it in a separate study folder only accessible to study personnel. An additional hard copy will be created and printed once per month and stored in a locker in our administrative office.

9 Safety

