11.1 Determination of Sample Size

Within a study period of 6 to 12 months, all elective and emergency patients scheduled for a Rapid Sequence Induction (RSI) will be included in this study. In 2019, a total of 2'718 general anaesthesias with Rapid Sequence Inductions (RSI) were undertaken at our institution. 275 thereof were children < 18 years of age. Further, 204 Rapid Sequence Inductions were performed in life threatening situations (category: Notfall <1h, vital, sofortiger Eingriff notwendig by the Swiss Society for Anaesthesiology and Resuscitation, A-QUA) where a delay is medically and ethically not acceptable. Further, we estimate that a number of 1000 patients per annum have one or more aspiration risk factors, receiving an advanced laryngeal mask or a regional anaesthesia. In conclusion, we aim to include at least 1500 up to 3200 patients in a one year recruitment period. On basis of the publication of Arzola et al.³⁶ individual differences in sonography performance can already be detected after 30 to 40 examinations. Although our residents will already have performed at least as many examinations before first patient inclusion, we postulate, that a similar number of patients per capita will be needed to investigate interindividual performance. Given an estimated number of 30 residents and 20 attendings participating, we aim to include 1500 - 2000 patients.

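### Section 8.1 does not keep the scan estimate from whoever suctions the stomach or judges tube placement, so the reference volume and the exclusions could follow the estimate

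*Protocol*

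**What the plan says.** Section 4.2 defines the primary endpoint as "Correlation of sonographic estimated gastric volume with volume aspirated through a naso- or oro-gastric tube, that was placed by routine". The aspirated volume is therefore the reference and the scan estimate is the measurement under test.

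Section 8.1 describes the sequence. The stomach is scanned; if fluid is seen, a volume is calculated from the right-lateral antral area and age by a fixed formula; after the routine tube is placed, "we compare the calculated and effective suctioned volume of the gastric content and analyse the difference and quality of the sonographic measurement". Care is given "by our usual anaesthesiologic team members". The sonography data "will be noted in a password protected Excel sheet only available to institute members by the responsible anaesthesiologist performing the examination". The scan result may also be acted on: "In exceptional cases the responsible anaesthesiologist is allowed to upgrade patients from an advanced laryngeal mask to an RSI after ultrasound performance".

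Section 7.2 excludes patients with "Contraindications for naso- or orogastric tubes or inability to correctly place such". Section 8.1 repeats this for tubes that are contraindicated or cannot be placed correctly: "In this case an exclusion of the study is mandatory according to our exclusion criteria".

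The protocol does not say who suctions, who judges placement, how placement is checked, or whether the estimate is entered before suction. It mentions no masking.

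**The concern.** The scan comes before suction, which protects the estimate from the aspirate. It does not protect the aspirate from the estimate. Two steps on the reference side are open to it.

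1. **Suction effort.** Someone who expects a certain amount may reposition and suction again when less comes, but not when the yield already matches.
2. **Exclusion.** A nearly dry tube after a scan that showed much fluid may be called misplaced. The same dry tube after a low estimate raises no question. Without a sign of placement that does not depend on the yield, the size of the disagreement could help decide who is analysed.

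Both would narrow the gap between estimate and reference. The primary correlation, the estimated-minus-aspirated difference, the >80% congruence standard and the learning curves all rest on that gap. Examiners also have a stake, because their own performance is being compared.

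**Working it through.** **The plan's own figure.** Section 11.1 takes it that "individual differences in sonography performance can already be detected after 30 to 40 examinations" and expects 30 residents and 20 attendings. (30 + 20) x 30 = 1500 and (30 + 20) x 40 = 2000, which reproduces its target of 1500 - 2000. The protocol gives no expected correlation, suction procedure or tube-failure rate. Everything below is therefore assumed and only shows orders of magnitude.

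**Model.** These inputs are assumptions:
- True volume V: lognormal, median 60 ml, log-SD 0.8.
- Estimate E = max(V + error, 0), with error SD 60 ml or 100 ml.
- Aspirate A = V x recovery, with recovery mean 0.85, SD 0.12, capped at 1.

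**Suction effort.** When A < E, extra suction closes a fraction f of the gap but cannot return more than the stomach holds: A' = min(A + f(E - A), V). Otherwise A' = A. For comparison, the unbounded rule A' = A + f(E - A) is applied to every pair.

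| Scan error SD | f = 0 | f = 0.1 | f = 0.2 | f = 0.3 |
|---|---|---|---|---|
| 60 ml, capped at V | 0.81 | 0.83 | 0.84 | 0.85 |
| 60 ml, unbounded | 0.81 | 0.85 | 0.89 | 0.92 |
| 100 ml, capped at V | 0.65 | 0.69 | 0.70 | 0.71 |
| 100 ml, unbounded | 0.65 | 0.74 | 0.81 | 0.87 |

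At SD 60 ml the unbounded rule puts the aspirate above the true volume in 18%, 28% and 34% of pairs, which suction cannot do. The capped rows are the usable ones.

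**Comparison with sampling error.** Fisher z, half-width 1.96/sqrt(1500 - 3) = 0.0507:
- r = 0.81: z = 1.127, 95% CI 0.79 to 0.83.
- r = 0.65: z = 0.775, 95% CI 0.62 to 0.68.

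The capped shifts are 0.02-0.04 and 0.04-0.06, about equal to or larger than the half-widths of roughly 0.02 and 0.03. The comparison uses 1500 pairs. The real number will be smaller, because a volume is calculated only for fluid content and regional anaesthesia patients receive no tube, so the intervals will be wider. A larger sample would not reduce the bias.

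**Exclusion.** Flag pairs with A < 50 ml and E - A > 50 ml, at SD 60 ml.
- No tube truly misplaced: dropping half of the flagged pairs removes 6% of all pairs, r goes from 0.81 to 0.83 and the mean overestimate falls from 19 to 15 ml. Dropping all of them removes 12% and gives 0.86 and 10 ml.
- Some tubes truly misplaced (assumed to recover 0-10% of V), half of the flagged pairs dropped: r is 0.82 at 3% misplaced, 0.81 at 5% and 0.79 at 10%, against 0.81 in correctly placed tubes.

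In this setting the exclusion effect runs from slight inflation through almost none to slight deflation. Another scan error or dropped share would give another answer. The deciding input, the true misplacement rate, is not in the documents.

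**The case against.** The strongest reply is that this is a possible bias, not an error, and that its premise is partly inferred. The protocol does not say that the examiner suctions, nor expressly that the millilitre figure is worked out before suction. Both points stand. A reader might infer that the same person does both and that the bias is present; the text supports neither. It does support that the responsible anaesthesiologist performs the scan, may act on the result, and belongs to the team that gives care, with nothing separating that knowledge from the reference measurement.

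Further suction after a low yield also recovers fluid that is really there. That stands as well: the fault is only that the effort could depend on the estimate. Stopping early once the expected amount has come would leave fluid in patients chosen for aspiration risk. No passage suggests it, and it is not in the capped model.

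Misplaced tubes should be excluded, because their aspirate is not a valid reference. A reader might infer that the rule as written selectively removes discordant pairs. It could, but the documents do not show that it does.

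Section 7 rules out changing established practice solely for the study. A uniform suction routine might breach that. Having a colleague read the volume and recording placement earlier need not.

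The point cannot be left to an unseen analysis plan. Who measures, and in what order, is fixed at the bedside and cannot be restored in the analysis.

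**Conclusion.** The point holds as a weakness of conduct in section 8.1. The reference for the primary endpoint, and one of the exclusions, are open to knowledge of the estimate, and the likely direction for suction effort is upward. With extra suction limited to the true volume, the assumed model gives r of 0.83-0.85 instead of 0.81, or 0.69-0.71 instead of 0.65. That is modest, but comparable with or larger than the sampling error at 1500 pairs. The exclusion effect may be near zero or even reversed, depending on the true misplacement rate.

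Larger claims, such as the unbounded rise from 0.65 to 0.87, should not be made, since they need more fluid than the stomach contains. All sizes rest on the assumed distribution, scan error, recovery and gap-closing fraction. The change is worth making because it is cheap and the validation claim depends on an independent reference.

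**What to change.** Amend section 8.1 as follows.

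(a) The estimate is entered before tube placement. Where possible, a usual team member already in the room who has not been told it suctions and records the aspirated volume. The responsible anaesthesiologist keeps the scan result, and pairs in which it had to be disclosed are flagged.

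(b) A yes/no field for correct tube placement is completed before the aspirated volume is known. Patients excluded for tube failure are counted and reported with their estimates.

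Tubes declared misplaced only after suction may be added back at most as a bounding sensitivity analysis, because their aspirate may be an invalid reference and could pull r down.

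The cost is protocol wording, one yes/no field, one disclosure flag and a line in the report. No extra procedure is needed, and no extra staff where a colleague is already present. The downside is that the examiner must not announce the estimate before suction. Masking will sometimes be incomplete, for example when the scan changes the airway plan. If the department's usual placement check itself relies on the aspirate, (b) protects less, and the protocol should say so.

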7.1 Inclusion Criteria

Subjects, who will fulfil all the following inclusion criteria, may be included into this project:

- All elective in-hospital Rapid Sequence Inductions (RSI) and patients with one or more aspiration risk factors scheduled for an advanced laryngeal mask or regional anaesthesia with informed consent.

- All emergency in-hospital RSI and patients with one or more aspiration risk factors scheduled for an advanced laryngeal mask or regional anaesthesia with informed consent graded as follows according to the Swiss Society for Anaesthesiology and Resuscitation (A-QUA): “Notfall 1-6h, nicht vital (dringlicher Eingriff)”, “Notfall 6-24h nicht vital (aufgeschobener dringlicher Eingriff)”

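### A gastric tube that cannot be placed after the scan removes the patient from the whole study, although endpoints that need no tube keep regional-anaesthesia patients who never have one

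*Protocol*

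**What the plan says.** **Who has a reference volume.** The primary endpoint (Protocol 4.2) is "Correlation of sonographic estimated gastric volume with volume aspirated through a naso- or oro-gastric tube, that was placed by routine". Section 7.1 also admits "patients with one or more aspiration risk factors scheduled for an advanced laryngeal mask or regional anaesthesia with informed consent". Section 8.1 describes the tube as one "which is a standard procedure for both RSIs and advanced laryngeal masks at our institution", and then states "Patients planned for an intervention in a regional anaesthesia will not receive a gastric tube".

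**What happens when the tube fails.** Section 7.2 lists as an exclusion criterion "Contraindications for naso- or orogastric tubes or inability to correctly place such". Section 8.1 repeats this for tubes that are contraindicated or cannot be placed: "In this case an exclusion of the study is mandatory according to our exclusion criteria". Tube failure is not among the withdrawal reasons in 7.3. That section does allow anonymous analysis of data already collected if a patient withdraws consent after the scan.

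**When a volume is calculated.** Under 8.1 the formula is applied only when the scan shows fluid. Content classed as empty, solid or mixed gets no calculated volume.

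**How many patients.** Section 11.1 starts from the 2019 count ("a total of 2'718 general anaesthesias with Rapid Sequence Inductions (RSI) were undertaken at our institution"), removes 275 children and 204 immediate vital emergencies, and adds an estimated "1000 patients per annum have one or more aspiration risk factors, receiving an advanced laryngeal mask or a regional anaesthesia". It separately aims for 1500 to 2000 patients, from 30 residents and 20 attendings at 30 to 40 examinations each.

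**The concern.** Two groups end up without an aspirated volume, and the plan treats them in opposite ways. A regional-anaesthesia patient never has a tube and remains a participant. A patient for RSI or laryngeal mask who has been scanned, but whose tube then cannot be placed, is removed altogether. Neither can enter the volume comparison, but both can supply everything that depends on the scan alone.

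Removing the second group makes study membership depend on something that happens after the observation of interest. The empty and full counts, examination times and management findings would then describe only those scanned patients whose tube later went in, plus regional patients. An aspiration in a patient with failed placement would also drop out of the total.

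The same gap affects how 11.1 can be read. The number of patients and the number of scans per examiner are given without saying how many will have both an estimated and an aspirated volume. The primary endpoint and the 80% agreement standard in 4.2 need both.

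**Working it through.** **A. The exclusion rule, section against section**

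1. Order of events. Section 8.1 has the volume calculated from the scan, then compared with what is suctioned once the tube is in. It also allows an upgrade of the airway plan after the ultrasound. The scan therefore precedes the tube. A contraindication may be known beforehand; failure of placement cannot be.
2. What each secondary endpoint needs. Learning performance against the 80% standard needs the aspirated volume. Empty and full counts, examination time, estimated risk against sonographic volume, management change and aspirations do not.
3. Treatment of patients without a tube on those tube-free endpoints: regional patients are kept, failed placements are removed.
4. Comparison with 7.3: data from a completed scan may be analysed after consent is withdrawn, but not, under 7.2 and 8.1, after a technical failure with consent intact.

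Size. The documents give no failure rate. Assume 2% to 10% of patients due for a tube, and 1500 to 2000 patients scanned.

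- No regional patients: 1500 × 0.02 = 30 to 1500 × 0.10 = 150; 2000 × 0.02 = 40 to 2000 × 0.10 = 200.
- Largest regional share (part B): 1037 × 0.02 = 21 to 1037 × 0.10 = 104; 1383 × 0.02 = 28 to 1383 × 0.10 = 138.

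Aspirations. Section 3.1 quotes an incidence of 0.01% to 0.8%. That is 1500 × 0.0001 = 0.15 to 2000 × 0.008 = 16 events. At the upper incidence, with 5% failure and independence assumed, 2000 × 0.008 × 0.05 = 0.8 events would be lost.

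**B. The counts in 11.1**

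Reproducing the plan's figures:

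- RSI pool: 2718 − 275 − 204 = 2239.
- With mask and regional patients: 2239 + 1000 = 3239, against the stated upper figure of 3200.
- Examiner-based aim: 50 × 30 = 1500 and 50 × 40 = 2000, exact.

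The split of the 1000 between mask and regional is not given. Let R be the number of regional patients, from 0 to 1000, and assume enrolment in proportion to the pool. The share without a tube is f = R / 3239, and the number due for a tube is N × (1 − f).

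| R (assumed) | f | of 1500 | of 2000 | per examiner, of 30 | per examiner, of 40 |
|---|---|---|---|---|---|
| 0 | 0% | 1500 | 2000 | 30 | 40 |
| 500 | 15.4% | 1268 | 1691 | 25.4 | 33.8 |
| 1000 | 30.9% | 1037 | 1383 | 20.7 | 27.7 |

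These are patients due for a tube, not paired volumes. Tube failures and non-fluid scans come off them, and the documents give no rate for either.

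**The case against.** The plan is open about regional patients having no tube, and enrolling them is legitimate because they serve several secondary endpoints. Which patients enter the volume comparison is an analysis-set question that a statistical analysis plan may settle. That stands. It does not cover the exclusion rule: the protocol itself fixes it as mandatory exclusion from the study, which an analysis plan cannot reverse.

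A reader might infer that regional patients undermine the sample size or leave the primary endpoint short of data. The documents do not support this:

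- Even if all 1000 were regional, the RSI pool of 2239 exceeds the aim of 1500 to 2000. The protocol makes no power claim that could fail.
- Only the upper figure of 3200 is built from the 1000. The 1500 to 2000 is examiners times scans. That regional patients can help fill it follows from their eligibility, not from a statement in 11.1.
- The 30 to 40 examinations come from a cited learning-curve study that, by section 8.1 and its title, concerned qualitative recognition of content. They are not clearly a number of tube-verified scans.
- R = 0 is within the possible range, and then the regional loss is nil.

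A reader might also infer that aspirations will be materially undercounted. Under the assumptions above, fewer than one lost event is expected. The case for keeping these patients rests on valid scan data and consistent rules; the aspiration count is a lesser reason. Independence may not hold, but the documents give nothing to quantify a link.

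**Conclusion.** The exclusion rule should be changed. It discards completed scans because of a later technical event, treats two untubed groups differently, and sits badly beside 7.3. This follows from the text alone; only the size (about 20 to 200 patients) depends on the assumed failure rate.

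The sample-size point is secondary and is one of description. The figures in 11.1 count all scans. Under proportional enrolment and a regional share anywhere from none to all of the 1000, between 1037 and 1500 of 1500 patients, or between 1383 and 2000 of 2000, would be due for a tube. The further loss from non-fluid scans applies to every group and cannot be sized from the documents. The effect falls on verified scans per examiner, and so on judging examiners against the 80% standard, more than on the overall correlation.

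**What to change.** 1. In 7.2 and 8.1, replace exclusion for failed tube placement with this rule: every scanned patient whose tube cannot be placed stays in all endpoints that need no tube and is left out of the volume comparison only, with the number of such patients reported as missing reference values. A contraindication known before the scan can remain an eligibility criterion.
2. In 11.1, say that 1500 to 2000 patients and 30 to 40 scans per examiner are total scans. Add the number of paired estimated and aspirated volumes expected, overall and per examiner, with the assumed regional share and the assumed proportion of scans showing fluid.

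Enrolment need not rise. Reserving the whole 1500 to 2000 for patients due for a tube would take up to 1500 / (1 − 0.3087) = 2170 to 2000 / (1 − 0.3087) = 2894 patients, and would still include scans with no calculated volume.

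The cost is protocol wording and a smaller, honest figure for verified scans. No new procedure, measurement or change in care is involved; the scan data already exist when the tube fails.
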